7.3.2 CAUTI/VAP

The statistical analysis for effectiveness is a Poisson regression with outcome measure rate of CAUTI/VAP per 1,000 central line days and with predictors sort of treatment (scrub-the-hub protocol or the disinfecting barrier cap) and time trend.

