3.1 Primary and Secondary Endpoints

3.1.1 Primary Endpoint: **The rate of compliance to hub disinfection protocol.**

3.1.2 Secondary endpoints (all collected from aggregate hospital surveillance data):

3.1.2.1 **Rate of central line associated bloodstream infections (CLABSIs) per 1,000 central line days**

3.1.2.2 **Catheter-Associated Urinary Tract Infection (CAUTI) per 1,000 catheter days and Ventilator-Associated Pneumonia (VAP) per 1,000 ventilator days (controls)**

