5.3.2 Efficacy Analyses

CLABSI

The statistical analysis for efficacy is a Poisson-regression with outcome measure rate of CLABSI per 1,000 central line days and with predictors sort of treatment (scrub the hub protocol or the disinfecting barrier cap), and variables for the time trend and the unit.

CAUTI/VAP

The statistical analysis for efficacy is a Poisson-regression with outcome measure rate of CLABSI per 1,000 central line days and with predictors

[name]

sort of treatment (scrub the hub protocol or the disinfecting barrier cap), and variables for the time trend and the unit.

[CLIN-PROT-ICH-US-05-319980](#), version 8, update to document (Protocol Amendment 2): Protocol amended to document addition of an ad-hoc analysis of CLABSI infections both pre- and post-intervention. CLABSI infections will be further classified as those associated with mucosal barrier injury (MBI), and those that are not MBI-related, using the current CDC NHSN definition of mucosal-barrier injury laboratory-confirmed bloodstream infection (MBI-LCBI). The analysis of the classified CLABSI infections (MBI and not MBI related) will be conducted separately using the same planned analysis as the overall aggregated CLABSI infections.

6. Data Handling and Record Keeping

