2.2 Endpoints

Primary endpoint

The rate of compliance to hub disinfection protocol.

Secondary endpoints

- Rate of central line associated bloodstream infections (CLABSIs) per 1,000 central line days;
- Catheter-Associated Urinary Tract Infection (CAUTI) per 1,000 catheter days and Ventilator-Associated Pneumonia (VAP) per 1,000 ventilator days (controls).

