5 PROTOCOL CLARIFICATIONS

In the protocol infections analysis were classified as efficacy analysis. Since this is a real-world study, in this SAP, these analyses will be classified as "Effectiveness analysis" instead of "Efficacy analysis".

In the effectiveness analyses, section 5.3.2 of the protocol, it is planned Poisson regressions for the measure rate of CLABSI and CAUTI/VAP per 1000 central line days with predictors sort of treatment (scrub-the-hub protocol or the disinfecting barrier cap), and variables for the time trend and the unit. In this SAP, it is planned two Poisson regressions for measure rate of CLABSI with all covariables (time trend, unit and sort of treatment). For the second Poisson regression model, since time trend variable and sort of treatment variable are dependent variables, this model will just include sort of treatment and unit. CAUTI and VAP infections

were only collected for the ICU unit/ward, in consequence, Poisson regression models will be performed, if applicable, with time trend and sort of treatment covariables.

Compliance calculation method of the period previous the intervention (scrub-the-hub) and after intervention (prospective period – needleless connectors compliance audits) are presented in section 9 - Data, derivations and transformations.

Infection rates calculation are presented in section 9 - Data, derivations and transformations.

Compliance by format of disinfecting cap (disinfecting cap strips vs. individual disinfecting caps) of the post-intervention period (prospective period) will be assessed. The type of caps used during the study was limited by unit ward. Only ICU unit ward was allowed to use disinfecting barrier cap strips, because of that the ICU post-intervention period compliance and the disinfecting barrier cap strips compliance results will be identical. On the other hand, individual disinfecting caps compliance will be calculated by the other unit wards (2^o floor, 3^o floor, 3^o floor – surgical ward, 4^o floor and 5^o floor). Please see section 9 Data, derivations and transformations.

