In the protocol section 5.1 – Datasets Analyzed, CAUTI and VAP data from the six months prior to the intervention will be analyzed and compared to data in the 6-month post intervention recording period to determine product effectiveness. In this SAP, CAUTI and VAP will not be compared between the pre-intervention period and the prospective period, because CAUTI and VAP infections assessments were only collected for ICU unit. Due to the lack of infections assessments in these two periods, only descriptive statistics will be presented.

In the protocol, it is described that the prospective compliance will include the observations of the number of needleless connectors with, and the number of needleless connectors without, disinfecting barriers caps attached. In this SAP for the prospective compliance will include also the observations of applicable ports with misused caps. In section 9 *Data, derivations and transformations* is presented the formula calculation for compliance rate for use of the disinfecting barrier cap on needleless connectors (post-intervention period).

In this SAP the CAUTI and VAP rates will be calculated using the number of CAUTI and VAP variables, instead of CLABSI variables as said in section 5.3.2 Efficacy Analysis of the protocol.

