$$\begin{aligned} & \text{CAUTI rate per 1000 catheter/days} \\ &= \frac{\text{Number of CAUTIs infections}}{\text{Number of indwelling urinary catheter days}} \times 1000 \end{aligned}$$

- **VAP rate per 1000 ventilator/days**

The following formula must be considered:

$$\text{VAP rate per 1000 ventilator/days} = \frac{\text{Number of VAPs infections}}{\text{Number of ventilator days}} \times 1000$$

- **Treatment**

A dichotomous variable will be calculated for CLABSI infections time period assessment.

Scrub-the-hub protocol – CLABSI infections detected during the first 6 months, pre-intervention period (retrospective period).

Disinfecting barrier cap – CLABSI infections detected during the last 6 months, post-intervention period (prospective period).

- **Compliance by format of disinfecting cap**

Compliance of disinfecting cap strips will be calculated using the previous formula “*Compliance rate for use of the disinfecting barrier cap on needleless connectors (post-intervention period)*” just with the ICU unit data.

Compliance of individual disinfecting cap will be calculated using the previous formula “*Compliance rate for use of the disinfecting barrier cap on needleless connectors (post-intervention period)*” using data of the following unit wards: 2^o floor, 3^o floor, 3^o floor – surgical ward, 4^o floor and 5^o floor.

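### The SAP both rules out and orders a pre/post comparison of CAUTI and VAP, and the model in SAP 7.3.2 names the wrong device days

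*SAP*

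**What the plan says.** On whether the two periods are compared:

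- SAP section 5 departs from protocol 5.1. Because CAUTI and VAP were collected only in the ICU, it says the two periods will not be compared on them and limits reporting to descriptive summaries.
- Earlier in the same section, the SAP says Poisson models for CAUTI and VAP, with treatment and time trend, will be run where applicable. It does not say when that is.
- SAP 7.3.2 specifies the model without any condition, with treatment (scrub-the-hub or barrier cap) and time trend as predictors.
- SAP 8.3 assigns table 5 to pre/post comparisons of CLABSI, CAUTI and VAP, table 12 to the CAUTI regression and table 13 to the VAP regression, again without a condition.

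On the denominator:

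- SAP 7.3.2 specifies a "Poisson regression with outcome measure rate of CAUTI/VAP per 1,000 central line days".
- The secondary endpoints in protocol 3.1.2.2 and SAP 2.2 use catheter days for CAUTI and ventilator days for VAP.
- The SAP section 9 formulas divide CAUTI by the "Number of indwelling urinary catheter days" and VAP by the "Number of ventilator days".
- Protocol 5.3.2 repeats the CLABSI text under its CAUTI/VAP heading: "Poisson-regression with outcome measure rate of CLABSI per 1,000 central line days".
- SAP section 5 responds that "CAUTI and VAP rates will be calculated using the number of CAUTI and VAP variables, instead of CLABSI variables", and also says that "Infection rates calculation are presented in section 9 - Data, derivations and transformations".

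**The concern.** The study is a before-and-after comparison with no concurrent control group. CAUTI and VAP are its named controls: protocol section 2 and SAP 2.1 use them to judge whether season or the hospital environment could explain a change in CLABSI. Two things about them are unsettled.

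First, the SAP does not settle whether the controls are formally compared. If that is decided only once results are available, the reader cannot tell whether a control comparison was planned or was kept or dropped because of what it showed. SAP section 1 gives limiting that kind of bias as a purpose of the document.

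Second, if the model is run as 7.3.2 words it, the modelled rate is not the endpoint and will not match the rate derived under section 9. A change in ventilator or urinary-catheter use relative to central-line use could then look like a change in infection risk.

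**Working it through.** **Step 1: the comparison.** The treatment term in 7.3.2 contrasts scrub-the-hub with the cap, which in this design means before against after. A model with that term is a pre/post comparison, so 7.3.2 and tables 5, 12 and 13 order what one paragraph of section 5 excludes. The conditional sentence in section 5 allows a reading in which the models are dropped when data are sparse. However, it has no criterion, and neither 7.3.2 nor 8.3 refers to it.

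**Step 2: the denominator.**

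| Place | CAUTI | VAP |
|---|---|---|
| Protocol 3.1.2.2, SAP 2.2 | catheter days | ventilator days |
| SAP section 9 | urinary-catheter days | ventilator days |
| SAP 7.3.2 | central line days | central line days |

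The likely source is the CLABSI text repeated in protocol 5.3.2. The section 5 correction replaces the infection counts and does not mention the days.

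**Step 3: possible size.** The plan states no figure to reproduce. It gives no device days and no CAUTI or VAP counts, so every input below is assumed. The set-up is one ICU and 12 monthly records (months 1–6 and 8–13, implementation month left out), with constant line days and a constant true infection rate per day of the correct device.

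*Level.* Rate per line day = true rate × (device days / line days).
- VAP: 10 per 1,000 ventilator days × 0.60 = 6 per 1,000 line days.
- CAUTI: 4 per 1,000 urinary-catheter days × 300/400 = 3 per 1,000 line days.

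*Ratio, abrupt step at cap introduction.* False rate ratio = (device days per line day, after) / (device days per line day, before). The treatment term absorbs the whole step. For ventilator days per line day:
- 0.60 to 0.55: 0.55/0.60 = 0.92
- 0.60 to 0.50: 0.50/0.60 = 0.83
- 0.60 to 0.45: 0.45/0.60 = 0.75

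*Ratio, gradual drift.* For a log-linear drift from 0.60 to 0.50 over months 1–13, the trend term takes all of it and the treatment ratio is 1.00. Without a trend term, each post month lies 7 months after its pre counterpart, so the ratio is (0.50/0.60)^(7/12) = 0.90. If the drift occurs only over months 7–13, the model with trend gives 0.996.

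*Correct offset.* With ventilator days as the offset, the ratio is 1.00 in every case.

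**Step 4: precision.** With n infections per period and treatment only, the 95% CI is the estimate multiplied or divided by exp(1.96 × √(2/n)). Adding the trend inflates the variance. The correlation of treatment with month is 21/√(182 × 3) = 0.899, so variance inflation is 1/(1 − 0.899²) = 5.20 and the standard error grows by √5.20 = 2.28.

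| n per period | treatment only | treatment + trend |
|---|---|---|
| 5 | 3.45 | 16.9 |
| 10 | 2.40 | 7.4 |
| 20 | 1.86 | 4.1 |

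The largest distortion in step 3 is a factor of 1/0.75 = 1.33. That is below every entry in the table.

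**The case against.** The best defence is that the denominator in 7.3.2 is a phrase carried over from the protocol and is governed elsewhere. Section 9 gives explicit formulas with the correct days, section 5 points to section 9 for infection rates, and both endpoint sections agree. An analyst who builds the rates from section 9 gets the right outcome. This stands as evidence of intent. It does not correct 7.3.2, the section that specifies the model's outcome and predictors.

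On the comparison, the conditional wording in section 5 and the sparse-data reason given in the same section can be read together as running the models only if the data support them. That also has force. A reader might infer that the SAP cannot be followed whichever way the analyst turns. The conditional sentence makes that too strong: the difficulty is a missing criterion and two sections that carry no condition. Nor does SAP section 6 settle the matter, since saying that CAUTI and VAP data will be analysed fits either option.

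The size argument is also fair. The false ratios need an abrupt shift in device use that coincides with cap introduction, and the documents give no reason to expect one. The level shift is a change of units that leaves the pre/post ratio alone. The table shells are an external document that was not available, so tables 5, 12 and 13 may already be narrower than SAP 8.3 says.

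**Conclusion.** The point holds as two inconsistencies in the current SAP text. Section 5 excludes a pre/post comparison of CAUTI and VAP that 7.3.2 and 8.3 order, and its conditional wording softens the conflict without resolving it. If the model is run, 7.3.2 also states an outcome that differs from the endpoints and from section 9.

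The practical effect is probably small. On the assumed inputs, a step from 0.60 to 0.50 ventilator days per line day gives 0.83, gradual drift gives 1.00 with the trend term, and the confidence interval is wider than either distortion at 5 to 20 infections per period. The same wide intervals show that section 5's worry about sparse data is sound. A reader might infer that the denominator would bias the study's conclusion about the cap. The documents do not support that: the primary endpoint is compliance, CLABSI has its own model and is correctly set on central line days, and both are unaffected.

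It should still be fixed, because these are the design's only control outcomes and the repair is a matter of wording.

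**What to change.** Before database lock, choose one of two options and make SAP sections 5, 7.3.2 and 8.3 and the table shells agree. Either is acceptable. Database lock is the deadline that SAP section 1 supports. Requiring the change before anyone has seen the infection data may not be achievable, since the pre-intervention figures come from existing hospital surveillance.

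- **(a) Keep the ICU pre/post models.** Rewrite 7.3.2 as two models: CAUTI counts with a log(urinary-catheter days) offset, and VAP counts with a log(ventilator days) offset. Delete the exclusion in section 5, and either define or delete the conditional wording. Report rate ratios with 95% CIs, labelled supportive and imprecise.
- **(b) Descriptive only.** Delete the 7.3.2 model, the section 5 sentence on these models, tables 12 and 13, and the CAUTI/VAP part of table 5. Report the section 9 rates by period. No offset edit is then needed, because section 9 already uses the right days.

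The cost is SAP wording and matching edits to the table shells. No new data are needed: section 9 already calls for the correct device days.

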2.1 Objectives

- To examine healthcare professionals' compliance to needleless connector antisepsis with the barrier cap protocol compared to the previous "scrub the hub" protocol;

- To establish the effect of the disinfecting barrier cap on the rate of Central Line Associated Blood Stream Infection (CLABSI) per 1,000 intravenous line days among the designated patient population.

Catheter-associated urinary tract infection (CAUTI) rates and ventilator-associated pneumonia (VAP) rates during the intervention period will also be reviewed to control for possible seasonal or environmental effects that may also influence CLABSI and hospital infection rates overall.

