7.3 Effectiveness Analyses

7.3.1 CLABSI

The statistical analysis for effectiveness is a Poisson regression with outcome measure rate of CLABSI per 1,000 central line days and with predictors sort of treatment (scrub-the-hub protocol or the disinfecting barrier cap), unit (ward) and time trend.

This analysis will also be performed by CLABSI infections associated with mucosal barrier injury (MBI) and not MBI-related.

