8.3 Infection assessments for the pre and post intervention period

The results regarding the infections assessments in the retrospective period (scrub-the-hub) and in the prospective period (use of the disinfecting barrier cap on needleless connectors) will be presented in tables 3 and 4 and listing 5 of the appendix.

CLABSI/CAUTI/VAP comparisons between pre-intervention and prospective periods will be presented in table 5 of the appendix.

Poisson regression results model for predicting rate of CLABSI infections, and by MBI, will be presented in table 6, table 7, table 8, table 9, table 10 and table 11 of the appendix.

Poisson regression results model for predicting rate of CAUTI infections will be presented in table 12 of the appendix.

Poisson regression results model for predicting rate of VAP infections will be presented in table 13 of the appendix.

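### CLABSI is modelled with and without the time trend but CAUTI and VAP only with it, so the no-trend CLABSI model has no control model of the same form, and SAP section 5 contradicts itself on whether the controls are compared at all.

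*SAP*

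**What the plan says.** **Purpose of the controls.** Under SAP 2.1, CAUTI and VAP "rates during the intervention period will also be reviewed to control for possible seasonal or environmental effects" that could also move CLABSI.

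**CLABSI models.** SAP section 5 says "it is planned two Poisson regressions for measure rate of CLABSI with all covariables (time trend, unit and sort of treatment"), then changes the second one: "since time trend variable and sort of treatment variable are dependent variables, this model will just include sort of treatment and unit". Section 7.3.1 describes only the version with the trend, its predictor list ending in "unit (ward) and time trend".

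**CAUTI and VAP models.** Both are collected in the ICU only. Section 5 says "Poisson regression models will be performed, if applicable, with time trend and sort of treatment covariables", and section 7.3.2 repeats this: "with predictors sort of treatment (scrub-the-hub protocol or the disinfecting barrier cap) and time trend". No version without the trend is mentioned.

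**Output.** In section 8.3 the CLABSI models "will be presented in table 6, table 7, table 8, table 9, table 10 and table 11". For the controls, "Poisson regression results model for predicting rate of CAUTI infections will be presented in table 12 of the appendix", and VAP has table 13. The same section puts period infection results in tables 3 and 4 and pre/post comparisons of all three infections in table 5.

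**The conflicting statement.** Further on, section 5 withdraws the pre/post comparison of CAUTI and VAP, on the ground that they come from the ICU alone and assessments are too few, and limits them to descriptive statistics.

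**The concern.** If dependence between trend and treatment is a reason to fit CLABSI without the trend, it applies equally to the controls, which are observed over the same months. The SAP gives no reason for treating them differently.

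The two forms answer different questions. Without the trend, any gradual change over the year goes into the treatment term. With the trend, the same change is moved out of it. A no-trend CLABSI estimate set beside a trend-adjusted control could therefore show that CLABSI moved and the controls did not, even when all three rates followed the same course. The controls are there to expose exactly that situation. The SAP does not name a main CLABSI model or say which CLABSI estimate is to be read against which control estimate.

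**Working it through.** The plan states no rate, event count or power, so there is no figure to reproduce. I compared the specifications and then calculated what the mismatch can do.

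**1. Models as specified**

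| Series | Wards | Treatment + trend | Treatment, no trend |
|---|---|---|---|
| CLABSI | ICU and five others | yes, with unit | yes, with unit (section 5 only) |
| CAUTI | ICU | yes, if applicable | not planned |
| VAP | ICU | yes, if applicable | not planned |

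Six CLABSI tables fit three outcomes (all, MBI, not MBI) times two models. That split is my inference, because the table shells are in a separate document.

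**2. Inputs**
- Six baseline and six recording months, with the first intervention month left out (SAP section 6). I number them 1–6 and 8–13, so the period midpoints are 10.5 − 3.5 = 7 months apart.
- Two-sided 5% level (SAP section 7).
- Assumed: equal device days each month; a trend linear in month on the log scale (the SAP does not define its form); a shared decline of 1 to 5% per month; no cap effect.

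**3. Treatment rate ratio under a shared trend**

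Without the trend term, and with equal device days, the rate ratio is (1 − d)^7 for monthly decline d:
- 0.99^7 = 0.93
- 0.98^7 = 0.87
- 0.97^7 = 0.81
- 0.95^7 = 0.70

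With the trend term, the expected treatment ratio is 1.00 in every case. The sign reverses if rates rise: 1.02^7 = 1.15 and 1.05^7 = 1.41, which count against the cap.

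**4. Cost of the trend term in precision**

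The sum of squares of month number within periods is 2 × 17.5 = 35, and between periods it is 12 × 3.5² = 147.
- r² = 147/182 = 0.81, so r = 0.90.
- VIF = 182/35 = 5.2, so the standard error is multiplied by √5.2 = 2.28.

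If the baseline instead ends before the initiation month, the gap is two months: VIF = (12 × 4² + 35)/35 = 6.5, a factor of 2.55. The two terms are strongly collinear, but both can be estimated.

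With an assumed 40 events in each period, the no-trend standard error is √(1/40 + 1/40) = 0.22. With the trend it is 0.22 × 2.28 ≈ 0.51. A 95% interval then spans a factor of exp(1.96 × 0.51) = 2.7 either way, so a trend-adjusted control that looks null says little.

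**5. Chance of p < 0.05 for treatment with no cap effect** (1,500 simulated single series per row; baseline events assumed)

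| Decline per month | Baseline events | No trend | With trend |
|---|---|---|---|
| 0% | 40 | 4% | 5% |
| 0% | 80 | 4% | 5% |
| 2% | 40 | 9% | 4% |
| 2% | 80 | 13% | 6% |
| 5% | 40 | 29% | 5% |
| 5% | 80 | 54% | 6% |

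**6. What the planned tables could supply**

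For one unit, with log device days as offset and treatment as the only term, the Poisson estimate is (Y₂/D₂)/(Y₁/D₁), where Y is events and D is device days. This is the crude ratio of pooled rates. If tables 3 to 5 show events and device days by period, a reader can compute the no-trend control estimate.

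**The case against.** The strongest reply is that the control information is not missing. Section 8.3 puts pre/post CAUTI and VAP comparisons in table 5, and by step 6 the crude ICU ratio is the estimate that a no-trend model would give. A reader might infer that no-trend CLABSI has no control of any kind, and the documents do not support that. What is missing is a control model of the same form, with a stated test or interval. Table 5 cannot be relied on to fill the gap while section 5 says that the comparison will not be made.

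A second reply is that section 7.3.1 keeps the trend, that the no-trend fit appears only in section 5 as the second of two, and that nowhere does the SAP say it will set a no-trend CLABSI estimate against a trend-adjusted control. This is correct. The misleading contrast is something the plan permits, not something it announces. It still permits it, because no rule ties each CLABSI estimate to a control.

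A third reply concerns direction. A reader might infer that the asymmetry favours the product. It does so only if rates fall; under rising rates the no-trend model works against the cap. The documents give no trend in either direction.

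**Conclusion.** The concern holds in a limited form. The no-trend CLABSI model lacks a control model of the same form, and section 5 contradicts sections 7.3.2 and 8.3, as well as its own earlier paragraph, on whether the controls are modelled and compared.

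Under a shared log-linear decline of 1 to 5% per month and equal device days, the mismatch alone can separate CLABSI from its controls by a ratio of 0.93 to 0.70 against 1.00. The distortion is small at the mild end of that range. A reader might take the simulated percentages as this study's false-positive rate. They are not: neither the event counts nor the trend are in the documents, and the result moves from 9% to 54% across the 2% and 5% declines shown.

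A reader might also infer that the trend-adjusted CLABSI model already has a like-for-like control. It shares the model form apart from the unit term, but pools six wards against ICU-only controls. Matching the trend term alone would therefore not make the series comparable.

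CLABSI is a secondary endpoint, but it carries the effectiveness conclusion, and the remedy is cheap.

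**What to change.** 1. Reconcile the section 5 statement that CAUTI and VAP are descriptive only and not compared with the models in sections 5 and 7.3.2 and with tables 5, 12 and 13 in section 8.3.
2. In sections 5, 7.3.2 and 8.3, fit CAUTI and VAP with both specifications, treatment plus trend and treatment only, each with a 95% confidence interval.
3. Fit ICU-only CLABSI with the same two specifications, so that one CLABSI estimate comes from the same ward as the controls.
4. Print each CLABSI estimate beside the control estimates from the same specification, and state that only like may be compared with like.

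The cost is SAP wording and a few short tables: one extra fit each for CAUTI and VAP and two for ICU CLABSI. No new data are needed, since incidence is already recorded by ward and month. The downside is that the ICU-only intervals will be wide, especially with the trend included, and the report should say so.
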